6.2.2 FOLLOW-UP

For sample scripts for all interactions with the dietitian for each arm of the study, see Appendices 9 (control arm), 10 (intervention arm), and 11 (exploratory arm).

Visit 4: Initial consultation with a dietitian (Day 0 +/- 6 working days)

- Perform 30-60 minute consultation with the dietitian
- Perform 24-hour recall of food intake for each participant.
- **Intervention and exploratory arms:** Provide NudgeBox experience whereby the participant will provide a buccal cheek swab to perform on-site rapid genotyping. This will provide the participant with a visualisation of how some of their genetic information is analysed

- **Control arm:** Provide NICE guidance by verbal and written communication as per standard care.
- **Intervention arm:** Provide DNA-based dietary information in verbal and written form to participants.
- **Exploratory arm:** Provide DNA-based dietary information via the DnaNudge App.

Visit 5: Follow-up phone-call with the dietitian (Day 14 +/- 6 working days) (Control and intervention arms only)

- Contact participants for a brief phone-call with the dietitian to address any dietary questions/problems.
- Perform 24-hour recall of food intake for each participant.

Visit 6: Glucose regulation review (Day 42 +/- 6 working days)

- Perform clinical assessment of glucose regulation and anthropometric measurements.
 - Obtain urine pregnancy test (if applicable).
 - Collect blood sample (15mL).
 - Assess blood pressure, weight, height, waist circumference, lean body mass, and fat body mass.
 - Perform 0 minutes on 75g glucose OGTT, 120 minutes on 75g glucose OGTT, 120 minutes c-peptide following 75g glucose OGTT, HOMA insulin sensitivity and secretion measurement.
 - Provide saliva sample (2mL) via spit.
- Complete FFQ

Visit 7: Follow-up phone-call with the dietitian (Day 56 +/- 6 working days) (Control and intervention arms only)

- Contact participants for a brief phone-call with the dietitian to address any dietary questions/problems.
- Perform 24-hour recall of food intake for each participant.

Visit 8: Glucose regulation review (Day 84 +/- 6 working days)

- Perform clinical assessment of glucose regulation and anthropometric measurements.
 - Obtain urine pregnancy test (if applicable).
 - Collect blood sample (15mL).
 - Assess blood pressure, weight, height, waist circumference, lean body mass, and fat body mass.
 - Perform 0 minutes on 75g glucose OGTT, 120 minutes on 75g glucose OGTT, 120 minutes c-peptide following 75g glucose OGTT, HOMA insulin sensitivity and secretion measurement.
 - Provide saliva sample (2mL) via spit.
- Complete FFQ.
- Complete trial completion questionnaire.

Visit 9: Follow-up phone-call with the dietitian (Day 84 +/- 6 working days) (Control and intervention arms only)

- Contact participants for a brief phone-call with the dietitian to address any dietary questions/problems.
- Perform 24-hour recall of food intake for each participant.

6.2.3 FINAL STUDY VISIT

Visit 10: Glucose regulation review (follow-up) (Day 182 +/- 6 working days)

- Perform clinical assessment of glucose regulation and anthropometric measurements.
 - Obtain urine pregnancy test (if applicable).
 - Collect blood sample (15mL).
 - Assess blood pressure, weight, height, waist circumference, lean body mass, and fat body mass.
 - Complete a food frequency questionnaire.
 - Perform 0 minutes on 75g glucose OGTT, 120 minutes on 75g glucose OGTT, 120 minutes c-peptide following 75g glucose OGTT, HOMA insulin sensitivity and secretion measurement.
 - Provide saliva sample (2mL) via spit.
- Complete FFQ
- Complete trial completion questionnaire.

Visit 11: Follow-up phone-call with the dietitian (Day 182 +/- 6 working days) (Control and intervention arms only)

- Contact participants for a brief phone-call with the dietitian to address any dietary questions/problems.
- Perform 24-hour recall of food intake for each participant.

6.2.4 EARLY TERMINATION VISIT

In the case of early termination, an interview will be conducted with the participant to determine reasons for termination if appropriate, and/or to determine if the data collected thus far may be useful.

6.2.5 Participant Testimonials

Once participants have completed their participation in the trial, they may be contacted by the Trial Team to see if they would like to provide a testimonial about their experience on the clinical trial. This may cover aspects including their experience using DnaNudge technology, aspects that they may have found useful, what is their opinion on DNA-based dietary guidelines, amongst others. Participants will consent to being contacted to see if they would like to provide a testimonial in the Informed Consent Form. Participant testimonials will allow for potential publication/media release either following the written consent of the participant. This may be in journals, newspapers, radio, interviews, TV, social media, websites, newsletters, marketing in print and online. When being asked to provide a testimonial, participants will be provided with a list of the above media types so that they can provide specific permission for which types of publication can be used. The testimonials will be published anonymously or with the participant's name, provided the participant has provided permission to do so.

6.2.6 SCHEDULE OF EVENTS TABLE

Activity	Trial Visit											Additional information
	1	2	3	4	5	6	7	8	9	10	11	
Send information documents to potential participants	x											
Consent		x										
Screening visit to assess glucose regulation		x										
Randomisation	x											
Fill in food frequency questionnaire	x				x		x		x			
Trial commencement questionnaire			x									All participants
Perform baseline measurements		x										
Take saliva sample for genetic testing (PCR)		x										
Initial consultation with dietitian			x									
Perform NudgeBox genetic test		x										
Provided with the DnaNudge App		x										Exploratory arm only
Follow-up phone-call with dietitian			x		x		x		x			Control and intervention arms
Perform 24-hour food recall		x	x		x		x		x			Control and intervention arms
6-week glucose regulation review				x								
Take saliva sample for leptin testing	x		x		x		x		x			
12-week glucose regulation review						x						
Trial completion questionnaire						x		x				
26-week glucose regulation review								x				
Weight measurement	x		x		x		x		x			
Height measurement	x		x		x		x		x			
Body composition	x		x		x		x		x			
Waist measurement	x		x		x		x		x			
Blood pressure	x		x		x		x		x			
Saliva sample (s)	x		x		x		x		x			
Venous blood test	x		x		x		x		x			
OGTT	x		x		x		x		x			
Pregnancy test (if applicable)	x		x		x		x		x			
Follow-up clinical visits				x		x		x				

Table 1: Schedule of events table for a trial participant.

7 ADVERSE EVENTS

7.1 DEFINITIONS

Adverse Event (AE): any untoward medical occurrence in a patient or clinical study subject.

Serious Adverse Event (SAE): any untoward and unexpected medical occurrence or effect that:

- **Results in death**
- **Is life-threatening** – refers to an event in which the subject was at risk of death at the time of the event; it does not refer to an event which hypothetically might have caused death if it were more severe
- **Requires hospitalisation, or prolongation of existing inpatients' hospitalisation**
- **Results in persistent or significant disability or incapacity**
- **Is a congenital anomaly or birth defect**

Medical judgement should be exercised in deciding whether an AE is serious. Important AEs that are not immediately life-threatening or do not result in death or hospitalisation but may jeopardise the subject, or may require intervention to prevent one of the other outcomes listed in the definition above, should also be considered serious.

7.2 REPORTING PROCEDURES

All adverse events should be reported. Depending on the nature of the event the reporting procedures below should be followed. Any questions concerning adverse event reporting should be directed to the Chief Investigator in the first instance.

7.2.1 NON SERIOUS AEs

All such events, whether expected or not, should be recorded.

7.2.2 SERIOUS AEs

An SAE form should be completed and sent to the Chief Investigator within 24 hours. However, relapse and death, and hospitalisations for elective treatment of a pre-existing condition do not need reporting as SAEs.

All SAEs should be reported to the North of Scotland REC 1 where in the opinion of the Chief Investigator, the event was:

- 'related', i.e. resulted from the administration of any of the research procedures; and
- 'unexpected', i.e. an event that is not listed in the protocol as an expected occurrence

Reports of related and unexpected SAEs should be submitted within 15 days of the Chief Investigator becoming aware of the event, using the NRES SAE form for non-IMP studies. The Chief Investigator must also notify the Sponsor of all SAEs.

Local investigators should report any SAEs as required by their Local Research Ethics Committee, Sponsor and/or Research & Development Office.

Contact details for reporting SAEs
Please send SAE forms to: [name]
[contact] (Mon to Fri 09.00 – 17.00)

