7.3 EXPECTEDNESS

The probability of adverse events is expected to be low given the single-centre nature of the study with a small cohort. The randomisation and diet allocation algorithms have been rigorously tested for misallocation.

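### Protocol 7.1 makes death a criterion for a serious adverse event, but 7.2.2 exempts death from SAE reporting with no limit by cause or relatedness

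*Protocol*

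**What the plan says.** Protocol 7.1 defines an SAE as "any untoward and unexpected medical occurrence or effect that" meets one of five listed criteria. The first is "Results in death", with no exception attached.

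Protocol 7.2 opens with a general rule, "All adverse events should be reported", and refers the reader to the procedures that follow. For non-serious events, 7.2.1 asks only for recording: "All such events, whether expected or not, should be recorded".

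For serious events, 7.2.2 requires an SAE form to reach the Chief Investigator within 24 hours. The next sentence is the exemption: "However, relapse and death, and hospitalisations for elective treatment of a pre-existing condition do not need reporting as SAEs". The section then gives the onward steps:

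- SAEs that the Chief Investigator judges related and unexpected go to the ethics committee within 15 days. Unexpected means "an event that is not listed in the protocol as an expected occurrence".
- "The Chief Investigator must also notify the Sponsor of all SAEs".
- Local investigators report SAEs as their own ethics committee, the sponsor or the R&D office requires.

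Protocol 7.3, on expectedness, says "The probability of adverse events is expected to be low given the single-centre nature of the study with a small cohort". It names no expected event.

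**The concern.** Two adjacent sections give opposite instructions for the gravest event the trial could record. One makes death an SAE; the other says it need not be reported as one. The exempting sentence also pairs death with *relapse*, a term that the protocol text supplied neither defines nor uses elsewhere, and that has no evident meaning in impaired glucose regulation.

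At stake is the expedited route. The 24-hour form is how the Chief Investigator is told of an SAE. The judgement of relatedness, the notice to the sponsor and the 15-day ethics report all follow from it. If site staff take the exemption at its word, the protocol does not require that chain to start.

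**Working it through.** The plan has no figure to reproduce, so the main check is textual. A short calculation then shows how often the rule could matter.

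**1. Is death an SAE under the protocol's own definition?** It meets the first criterion in 7.1. The definition also requires the event to be unexpected. By the test in 7.2.2, an event is unexpected unless the protocol lists it as expected. Section 7.3 lists none, so on the text supplied every death is unexpected and qualifies as an SAE. The contents of the appendices were not available to check.

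**2. Does the exemption cover only some deaths?** The limit to elective treatment of a pre-existing condition belongs to hospitalisations. Nothing in the sentence limits death to expected, unrelated or disease-related cases. By step 1, it cannot be explained as covering expected deaths, because none are listed.

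**3. What does the exemption remove, read literally?**

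| Duty in 7.2.2 | Applies to | A death, under the exemption |
|---|---|---|
| Form to the Chief Investigator, 24 hours | SAEs | not required |
| Ethics committee report, 15 days | related and unexpected SAEs | not required, even if related and unexpected |
| Notice to the sponsor, no time limit stated | all SAEs | not required |

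Two things should not be blamed on the exemption. Unrelated deaths would not go to the ethics committee without it either, and the missing time limit for the sponsor notice is a separate matter.

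**4. Does other text restore the route?**

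- The general rule in 7.2 means that deaths are not outside all reporting, but it sets no deadline and hands over to the procedures below, where the exemption sits.
- Section 7.2.1 covers only non-serious events and asks only for recording.
- Section 11.1 has adverse event data entered with the clinical data, again with no expedited step.
- The monitoring plan mentioned in 12.1 was not supplied, so it could not be checked.
- The SAP adds nothing. Its contents list has no safety section, and the participant-flow table in SAP 1.7.1 counts losses to follow-up and withdrawals but names no category for deaths. The flowchart figure was not visible.

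**5. Size.**

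Inputs: 180 participants (Protocol 9.2); final visit at Day 182 (6.2.3); screening from Day -42 at the earliest (6.2.1). Mortality of 1 to 10 per 1,000 person-years is an assumption; the documents give no figure.

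- Person-years = participants × days / 365.25
- From Day 0: 180 × 182 / 365.25 = 89.7
- From Day -42: 180 × (182 + 42) / 365.25 = 180 × 224 / 365.25 = 110.4
- Expected deaths, low end: 89.7 × 0.001 = 0.09
- Expected deaths, high end: 110.4 × 0.010 = 1.10
- P(at least one) = 1 − exp(−expected): 1 − exp(−0.0897) = 0.086, and 1 − exp(−1.104) = 0.668

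These figures use nominal visit dates and no drop-out. Visit windows and the extension for a suspension under 12.2 would lengthen exposure; drop-out would shorten it.

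**The case against.** The strongest reply is that the exemption says only that deaths need not be *reported* as SAEs, not that they stop *being* SAEs. The later sentences on the ethics report and the sponsor notice carry no exception, so a reader could hold that a related, unexpected death still goes to both. That reading is available. It does not settle the matter, because the same subsection then says two contrary things. It also depends on the Chief Investigator learning of the death by some route other than the form that the exemption removes.

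There are also softer safeguards. This is a single-site trial, 7.2 directs reporting questions to the Chief Investigator, local reporting requirements still apply, and under section 12 a steering committee that includes the Chief Investigator meets at least quarterly. These make it unlikely that a death would go unnoticed, and this point does not claim that it would. None of them sets a 24-hour or 15-day limit.

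The objection to the size is partly right. The 9% to 67% range is for death from any cause, so it bears on the SAE form and the sponsor notice. The chance of a related, unexpected death is smaller by an unknown amount. The upper end also combines the highest assumed mortality with the longest nominal exposure for every participant, in a population from which several serious illnesses are excluded.

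Finally, *relapse* is not a criterion in 7.1, so it is not part of the contradiction. Removing it is still harmless: any such event would simply be judged against the ordinary seriousness criteria.

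**Conclusion.** The contradiction is real, lies in current text, and is not resolved anywhere in the documents supplied. It must be fixed. Read literally, 7.2.2 leaves a related and unexpected death with no mandated SAE form and no mandated ethics report; read the other way, it contradicts its own exemption. That conclusion rests on the wording alone and not on the assumed mortality, which only indicates that at least one death of any cause during the trial is plausible. The defect concerns safety reporting only. The sample size, the error rates and the primary comparison do not depend on it.

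**What to change.** Delete *relapse and death* from the exempting sentence in 7.2.2, leaving hospitalisation for elective treatment of a pre-existing condition as the only exemption. Deaths then take the route already written there: the 24-hour form, a judgement of relatedness, notice to the sponsor, and a 15-day ethics report where the death is related and unexpected. No new procedure is needed.

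The cost is a one-phrase amendment, a note to staff and, on the assumed mortality, an expected 0.1 to 1.1 extra SAE forms over the whole trial. That is an average and not a ceiling: at the upper end, the chance of two or more deaths is 1 − exp(−1.104) × (1 + 1.104) = 0.30.

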7.3 EXPECTEDNESS

The probability of adverse events is expected to be low given the single-centre nature of the study with a small cohort. The randomisation and diet allocation algorithms have been rigorously tested for misallocation.

8 ASSESSMENT AND FOLLOW-UP

For each participant, follow-up measurements will be taken at 26 weeks. This will include all of the secondary outcomes outlined above. Participants will then complete a questionnaire (see Appendix 4) at the conclusion of the study to collect information regarding their experience of the intervention.

The study will be complete when the 26 week follow-up measurements are taken for the final participant in the trial.

9 STATISTICS AND DATA ANALYSIS

9.1 ANALYSIS DATASETS

Primary analyses will be conducted following the intention to treat (ITT) principle. All participants who are randomised into the study will be included in the ITT analysis. Such participants constitute the Full Analysis Set (FAS) for this study. In addition, the primary endpoint and the main secondary outcomes will also be analysed with the Per Protocol Analysis Set (PPS), which will consist of those subjects in the FAS who complete the study with no significant deviations from the planned protocol procedures.

9.2 THE NUMBER OF PARTICIPANTS

The total number of participants recruited into the study will be 180. All arms of the trial will have 60 participants each.

Participants will be recruited in cohorts of $N = 60$. Each member of a given cohort will be randomly allocated into one of the three arms of the study, as per the blocked randomisation method outlined below. The subdivision of the recruitment process into cohorts has been implemented in order to:

1. Allow sufficient time to perform the genetic analysis to prepare the DNA-based diet for the participants allocated to the intervention and the exploratory arms.
2. Ensure that the data collected is of sufficient quality. If data in the first cohort of 60 participants is not deemed to be of sufficient quality, appropriate changes will be made to ensure that useful data is obtained from subsequent trial participants.
3. To prevent delayed commencement of the study due to recruitment capacity.

Upon enrolment into the trial, each participant will be assigned to a study arm based on stratified, blocked randomisation. A block size of 15 will be employed, using the stratifications and allocation size according to age and gender shown in [Table 2](#).

	Control arm	Intervention arm	Exploratory arm
Women (age <= 40)	5	5	5
Women (age > 40)	5	5	5
Men (age <= 40)	5	5	5
Men (age > 40)	5	5	5

Table 2: Allocation categories and size for the stratified blocked randomisation of participants.

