given permission via their direct care team. If the potential participant is considered eligible by any of the above methods, they will be contacted via email or telephone by the clinical trial team to ask them if they would like to undergo a screening test at the clinical research facility to assess their suitability for the trial.

Given the high rate of diagnosis of diabetes and pre-diabetic individuals by the North-West London GP network in 2016, we anticipate the accrual rate for N = 180 pre-diabetic individuals to fulfil our planned recruitment schedule of N = 60 participants every 3 months.

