### **1.14 Planned analysis**

The primary analysis will be conducted under the ITT principle using modified ANCOVA as described above. Raw and adjusted mean differences in PFG at week 6 between the intervention and control arm will be presented with 95% confidence interval (95% CI). The adjusted mean difference will be estimated using a linear regression model of week 6 FPG to baseline PFG and treatment arm adjusted for age and sex.

The primary null hypothesis is of no difference in week 6 FPG adjusted means between the intervention and the control arms. It will be tested against the alternative hypothesis of a difference between the two groups.

$$H_0: \mu_0 = \mu_1$$

$$H_A: \mu_0 \neq \mu_1$$

Where  $\mu_0$  and  $\mu_1$  are the week adjusted trimmed mean FPG in respectively the control and intervention group. The null hypothesis will be rejected if the robust adjusted 95% CI of the mean difference does not include 0.

- Power of the analysis

With 60 participants in each group and assuming that the average PFG changes from baseline to the week 6 will be -0.6 mmol/l in the intervention arm and -0.1 mmol/l in the control arm, that the baseline standard deviation (sd) of PFG is 0.7, the post-intervention sd is 0.6, and that the correlation between baseline and post-intervention measurement range between 0.6 and 0.4, the analysis will have a power greater than 0.9 to detect a difference between both arms.

- Sub-group and additional analysis of the primary outcome

An interaction between baseline FPG and treatment effect will be tested.

No sub-group analysis is planned for the primary endpoint.

- Sensitivity analysis

The robustness of the results will be tested using a non-parametric model as described above.

Both results will be presented and discrepancies will be discussed.

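### Arms are randomised within recruitment cohorts of 60, but no model names cohort, so the confidence interval may be slightly wider than the design requires

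*Protocol*

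**What the plan says.** Protocol 9.2 sets the overall size ("The total number of participants recruited into the study will be 180"), recruits in cohorts of 60, and randomises inside each: "Each member of a given cohort will be randomly allocated into one of the three arms of the study". The number of cohorts is not stated; 180/60 gives three. Their spacing comes from Protocol 4.4: "planned recruitment schedule of N = 60 participants every 3 months".

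On the allocation method, Protocol 9.2 says: "A block size of 15 will be employed, using the stratifications and allocation size according to age and gender". Table 2 has four age-by-sex strata of 15, which sum to 60. It therefore appears to describe one cohort, with 20 participants per arm per cohort if every block fills.

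One stated purpose of the cohorts is a check on data quality: "If data in the first cohort of 60 participants is not deemed to be of sufficient quality, appropriate changes will be made" for the participants who follow. The changes are conditional and are not described.

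The primary analysis in SAP 1.14, in the same terms as Protocol 9.4, is a "linear regression model of week 6 FPG to baseline PFG and treatment arm adjusted for age and sex". Protocol 9.4 adds an interaction between baseline glucose and arm. SAP 1.9 uses the same covariates for the other continuous outcomes. The mixed model in SAP 1.10 lists generic covariates, and the rank tests in SAP 1.11 take none. Neither document names cohort or recruitment period as a covariate, stratum or random effect.

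**The concern.** Age and sex structure the allocation, and both are in the model. Cohort also structures the allocation and is not. Cohorts enrolled about three months apart can differ in mean glucose through season, case mix or a change in data collection, and Protocol 9.2 itself foresees the last of these. When each cohort contains all arms, such a difference can be separated from the treatment comparison by a cohort term. Without one, the unexplained part is counted as random error.

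What is at stake is precision: a wider interval, a test whose true size falls below its nominal 5%, and a residual SD that is somewhat too large as a planning figure for a later trial. The last matters a little because this is labelled a pilot.

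**Working it through.** **Inputs from the documents.** SAP 1.14: baseline SD 0.7, week-6 SD 0.6, correlation 0.4 to 0.6, difference 0.5 mmol/L (−0.6 against −0.1), 60 per arm. Alpha is 5%, two-sided (Protocol 9.4, SAP 1.20).

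**Assumed input.** A residual shift s in one cohort of three, after baseline adjustment, of 0.2, 0.3 or 0.4 mmol/L. The documents give no value.

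**1. The SAP's power statement.** ANCOVA residual SD = 0.6 × √(1 − ρ²): 0.55 at ρ = 0.4 and 0.48 at ρ = 0.6. With 60 per arm and a difference of 0.5, the two-sample t calculation gives power 0.9986 and 0.9999. The SAP's claim of more than 0.9 is reproduced.

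**2. Variance added by an unmodelled shift.** One cohort in three differing by s adds s² × (1/3) × (2/3) = (2/9)s². Divide by the residual variance, 0.3024 (ρ = 0.4) or 0.2304 (ρ = 0.6). The standard error grows by the square root of one plus that ratio.

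| s (mmol/L) | Added variance | Rise in residual variance | Rise in standard error | Power at SD 0.55, 60 per arm |
|---|---|---|---|---|
| 0 | 0 | 0 | 0 | 0.9986 |
| 0.2 | 0.0089 | 2.9–3.9% | 1.5–1.9% | 0.9982 |
| 0.3 | 0.0200 | 6.6–8.7% | 3.3–4.3% | 0.9976 |
| 0.4 | 0.0356 | 11.8–15.4% | 5.7–7.4% | 0.9967 |

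With 50 evaluable per arm and SD 0.55, power goes from 0.9945 with no shift to 0.9892 at s = 0.4. At SD 0.48 it stays at or above 0.9977 even with 50 per arm.

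**3. How much of a raw shift survives baseline adjustment.** If a cohort is shifted equally at baseline and week 6, the baseline covariate removes a fraction equal to its slope, ρ × 0.6/0.7 = 0.34 to 0.51. So 49 to 66% remains. A residual shift of 0.2 then needs a raw common shift of 0.2/0.66 to 0.2/0.49, about 0.30 to 0.41 mmol/L. A residual shift of 0.4 needs about 0.61 to 0.82. In the SAP's change-from-baseline model (SAP 1.9) a common shift cancels. Only a shift arising between a cohort's own baseline and week-6 visits stays in full.

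**4. Simulation check.** 4,000 runs of least-squares ANCOVA, ρ = 0.5, 20 per arm per cohort, cohort 1 against cohorts 2 and 3. Age and sex were left out, and the SAP's robust estimator was not used.

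| Step | SE without / with cohort | Type I error without / with cohort |
|---|---|---|
| 0.3, week 6 only | 0.099 / 0.095 | 0.040 / 0.048 |
| 0.5, week 6 only | 0.104 / 0.095 | 0.032 / 0.047 |
| 0.5, both visits | 0.098 / 0.095 | 0.043 / 0.048 |

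The mean estimate was about −0.50 in every case, so there is no bias. Power was 0.999 or higher with and without the cohort term in all three.

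**The case against.** The strongest reply is that nothing here threatens validity. Randomisation within cohort protects the estimate, the error is in the conservative direction, and primary power is close to 0.99 or higher under every assumed shift. All of that stands.

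It is also fair to say that the size rests on an assumption. Changes made for later participants would usually affect their baseline and week-6 visits alike, and part of that is absorbed. A residual shift of 0.4 mmol/L would then need a raw shift at least as large as the whole week-6 SD of 0.6. So 0.4 is a generous upper value.

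Protocol 9.4 also lets unnamed relevant baseline covariates be explored and kept if significant. Cohort could enter that way, but it is not named, and a term chosen because it proved significant is not prespecified. This answers the point only in part.

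Four stronger readings are tempting, and the documents support none of them:

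- *Cohort shifts stay wholly in the error term.* They do not; see step 3.
- *A cohort term would show whether the effect holds after a change in data collection.* A main effect cannot show that. It needs a cohort-by-arm comparison, and at 20 per arm the 95% half-width in one cohort is 2.02 × SD × √(2/20) = 0.31 to 0.35 mmol/L, against an effect of 0.5. SAP 1.14 plans no subgroup analysis of the primary endpoint.
- *Procedures will change after cohort 1.* Protocol 9.2 makes any change conditional on poor data quality and does not mention glucose measurement.
- *Cohort 1 might be left out of the analysis.* Protocol 9.1 and SAP 1.6 already place everyone randomised in the intention-to-treat set.

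**Conclusion.** The point holds as a minor matter of precision. The trial randomises within a grouping that no model names. The effect estimate is unbiased; the interval is somewhat too wide and the test conservative to the extent that cohorts differ after baseline adjustment. For assumed residual shifts of 0.2 to 0.4 mmol/L in one cohort, the standard error is about 1.5 to 7% larger than necessary, with negligible loss of primary power.

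This rests on three cohorts of equal size with near-equal arms in each, the SAP's SDs and correlations, and a least-squares approximation to the robust fit. If cohorts do not differ, nothing is lost by the present plan. The documents give no power calculation for the secondary outcomes, so the reassurance about power applies to the primary endpoint only.

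**What to change.** Add recruitment cohort, as a three-level fixed factor set at enrolment, to the covariates in SAP 1.9 (ANCOVA), 1.10 (mixed models) and 1.14 (primary analysis), and to the matching text in Protocol 9.4. That covers the primary and secondary ANCOVA and the mixed models. The rank tests are unaffected.

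The cost is a sentence or two of wording and two degrees of freedom. The primary model has 120 − 5 = 115 residual degrees of freedom (intercept, arm, baseline, age, sex), which would become 113. In the simulation with no cohort shift, the standard error was 0.095 with and without the term. Cohort is known for every participant, so no new data are needed.
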